### **Step 6: Scoring the physical and mental component summary measures using health domain z scores**

The Physical Component Summary (PCS) and Mental Component Summary (MCS) measures are then scored using a three-step procedure, regardless of whether a standard or acute form was administered. First, the eight health domain scales are standardized using means and standard deviations from the 2009 U.S. general population. Second, these standardized scores are aggregated using weights (factor score coefficients) from the 1990 US general population. Computation of an aggregate physical component score consists of multiplying each health domain scale z-score by its respective physical factor score coefficient and then summing the eight products. Similarly, an aggregate mental component score is obtained by multiplying each health domain scale z-score by its respective mental factor score coefficient and summing the eight products. To illustrate, a portion of the formula for aggregating scales when estimating a standard form of aggregate mental component score is as follows:

$$\text{Aggregate mental component score} =$$

$$(PF\ z - \text{score} \times -0.22999) \dots + (MH\ z - \text{score} \times 0.48581)$$

Third, aggregate PCS and MCS scores are standardized using a linear T-score transformation with a mean of 50 and a standard deviation of 10. The formulas for computing the norm-based T score for each component summary measure are:

$$PCS\ T\text{-score} = 50 + (\text{Aggregate physical component score} \times 10)$$

$$MCS\ T\text{-score} = 50 + (\text{Aggregate mental component score} \times 10)$$

### **Step 7: Scoring the response consistency index (RCI)**

The Response Consistency Index (RCI) is optional, but is a simple and easy way to evaluate the consistency of responses to individual survey items. The RCI comprises of 15 pairs of items and assesses each pair for consistency. If a pair of responses is consistent, then the

RCI score for that pair would be 0. Conversely, a pair of inconsistent responses would earn a score of 1. For example, if a respondent indicates that he or she can “walk more than a mile” but, at the same time, cannot “walk 100 yards,” then this item pair would be considered inconsistent and would earn 1 RCI point. For a given respondent, the final RCI score is the sum of the scores earned on the 15 consistency checks. Thus, the best (i.e., most consistent) RCI score is 0 and the worst (i.e., least consistent) score is 15. Note that it is not necessary for a respondent to have complete data for all 15 pairs to compute the RCI (pairs with missing or out-of-range data are not used in the final calculation). However, if all 15 pairs have missing data for one or both items, then the RCI for that respondent cannot be scored.

### **EuroQol 5 dimension, 3 level quality of life questionnaire (EQ-5D-3L)**

The EQ-5D-3L questionnaire is made up for two components; health state description and evaluation.

As to the health state description, the EQ-5D-3L descriptive system contains 5 categories (mobility, self-care, usual activities, pain/discomfort, and anxiety/depression). Each category contains three responses choices: top (having no problems), middle (having some or moderate problems), and bottom (being unable to do/having extreme problems). The top response choice is coded as “1”, the middle response choice as “2”, and the bottom response choice as “3”; while ambiguous values (e.g. multiple boxes ticked for one category) are treated as missing values, which are coded as “9”. As a result, a person's health status can be defined by a 5-digit number, ranging from 11111 (having no problems in all dimensions) to 33333 (having extreme problems in all dimensions). For example, 12321 indicates having no problems in mobility and anxiety/depression, having slight problems in self-care and pain/discomfort, and having extreme problems in usual activities. Thus, there are potentially 243 (=3) different health states.

Visual analogue scale (VAS) is the second part of the questionnaire, asking to mark health status on the day of the interview on a 20 cm vertical scale with end points of 0 and 100. There are notes at the both ends of the scale that the bottom rate (0) corresponds to “the worst health you can imagine”, and the highest rate (100) corresponds to “the best health you can imagine”. The respondents have to draw a line from the box on the questionnaire to the scale indicates the health state of the interviewed day; while ambiguous values (e.g. the line crosses the VAS twice) should be treated as missing values, which are coded as “999”. Eventually, the EQ-5D-3L results can be converted into a single index value; many different terms are in use for these

index values, such as preference weights, preference-based values, utilities, QALY weights, etc.

### **Work Productivity and Activity Impairment (WPAI)**

WPAI outcomes are expressed as impairment percentages, with higher numbers indicating greater impairment and less productivity (i.e., worse outcomes) as follows:

#### **Questions**

Q1 = currently employed

Q2 = hours missed due to specified problem

Q3 = hours missed other reasons

Q4 = hours actually worked

Q5 = degree problem affected productivity while working

Q6 = degree problem affected regular activities

#### **Scores**

Multiply scores by 100 to express in percentages.

- Percent work time missed due to problem  

$$Q2 / (Q2+Q4)$$

- Percent impairment while working due to problem  

$$Q5 / 10$$

- Percent overall work impairment due to problem

$$Q2/(Q2+Q4)+[(1-Q2/(Q2+Q4)) \times (Q5/10)]$$

- Percent activity impairment due to problem  

$$Q6 / 10$$

### **Patient Treatment Satisfaction Questions**

The patient treatment satisfaction questions were developed de novo for this study and are not considered “validated” questions. There are totally 4 questions asking about the patients’ satisfaction with the following 4 aspects respectively:

1. The way RA treatment improves the morning stiffness in and around the joints.

2. The way RA treatment improves the mobility.
3. The way RA treatment improves the ability to perform daily living requiring fine motor skills.
4. The overall RA treatment.

There are totally 5 responses for each of the question: very satisfied, somewhat satisfied, neither satisfied nor dissatisfied, somewhat dissatisfied, and very dissatisfied.

### **3.5.2 Exposure/Independent Variables of Interest**

- **Patient demographics (if data available)**
  - Date of birth
  - Age at baseline
  - Age groups
  - Gender at birth
  - Marital status (married, unmarried)
  - Medical plan type
    - ✓ The type of healthcare plan each patient is enrolled in at baseline will be determined, including National/Public insurance, Private insurance, Employer benefits, and Other
- **Clinical characteristics**
  - Initial Diagnosis of Rheumatoid Arthritis (RA)
    - ✓ Year of initial diagnose
  - Initiation of Adalimumab
    - ✓ First time administration (DD/MM/YYYY)
    - ✓ Dosage of first injection (in mg)
  - Disease status of RA
    - ✓ Moderate (defined as Disease Activity Score in 28 Joints (DAS28) between 3.2 and 5.1)
    - ✓ Severe (DAS28>5.1)
  - Erythrocyte sedimentation rate (ESR) (in mm/hour)
  - C reactive protein (CRP) (in mg/L)
  - Disease Activity Score in 28 joints (DAS28)

To calculate the DAS28, the physician or specialist nurse will:

1. Count the number of swollen joints (out of the 28)

2. Count the number of tender joints (out of the 28)
3. Take blood to measure the erythrocyte sedimentation rate (ESR) or C reactive protein (CRP); the latest measurement in the medical records may also be used if a blood draw is not standard for that visit
4. Ask the patient to make a 'global assessment of health' which will be indicated by marking a 10 cm line between very good and very bad

The physician or specialist nurse will then mark each component score on the CRF and the DAS28 score if calculated (an online scoring calculator for the DAS28 can be found at <http://www.das-score.nl/das28/DAScalculators/dasculators.html>).

The DAS28 will be scored using the following formula:

$$\text{DAS28} = 0.56 * \text{sqrt}(\text{tender28}) + 0.28 * \text{sqrt}(\text{swollen28}) + 0.70 * \ln(\text{ESR or CRP}) + 0.014 * (\text{Global assessment of Health})$$

DAS28 scores will be interpreted using the following categorization:

- ✓ Remission:  $\text{DAS28} \leq 2.6$
  - ✓ Low Disease Activity:  $2.6 < \text{DAS28} \leq 3.2$
  - ✓ Moderate Disease Activity:  $3.2 < \text{DAS28} \leq 5.1$
  - ✓ High Disease Activity:  $\text{DAS28} > 5.1$
- comorbidities
- ✓ Myocardial infarction
  - ✓ Congestive heart failure
  - ✓ Peripheral vascular disease
  - ✓ Cerebrovascular disease
  - ✓ Dementia
  - ✓ Chronic pulmonary disease
  - ✓ Connective tissue disease
  - ✓ Ulcer disease
  - ✓ Mild liver disease
  - ✓ Diabetes
  - ✓ Hemiplegia
  - ✓ Moderate or severe renal disease
  - ✓ Diabetes with end-organ damage
  - ✓ Any tumor
  - ✓ Leukemia
  - ✓ Lymphoma
  - ✓ Moderate or severe liver disease

- ✓ Metastatic solid tumor
- ✓ AIDS

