9.2.4.7 Study Documents

Clinical case report form (CRF)

The clinical CRF will document the patient's current status (moderate, severe RA), Disease Activity Score in 28 joints (DAS28), prior and current treatments and other relevant clinical and demographic data to be used in segmenting the population during analysis.

To calculate the DAS28 the physician or specialist nurse will:

1. Count the number of swollen joints (out of the 28)
2. Count the number of tender joints (out of the 28)
3. Take blood to measure the erythrocyte sedimentation rate (ESR) or C reactive protein (CRP); the latest measurement in the medical records may also be used if a blood draw is not standard for that visit
4. Ask the patient to make a 'global assessment of health' which will be indicated by marking a 10 cm line between very good and very bad

The physician or specialist nurse will then mark each component score on the CRF and the DAS28 score if calculated (an online scoring calculator for the DAS28 can be found at <http://www.das-score.nl/das28/DAScalculators/dasculators.html>).

The DAS28 will be scored using the following formula:

$$\text{DAS28(CRP)} = 0.56 * \text{sqrt}(\text{tender28}) + 0.28 * \text{sqrt}(\text{swollen28}) + 0.36 * \ln(\text{CRP}+1) + 0.014 * (\text{Patient Global assessment of Health in mm})+0.96$$

$$\text{DAS28(ESR)} = 0.56 * \text{sqrt}(\text{tender28}) + 0.28 * \text{sqrt}(\text{swollen28}) + 0.70 * \ln(\text{ESR}) + 0.014 * (\text{Patient Global assessment of Health in -mm})$$

DAS28 scores will be interpreted using the following categorization:

- Remission: $\text{DAS28} \leq 2.6$
- Low Disease activity: $2.6 < \text{DAS28} \leq 3.2$
- Moderate Disease Activity: $3.2 < \text{DAS28} \leq 5.1$
- High Disease Activity: $\text{DAS28} > 5.1$

The full CRF is presented in **Error! Reference source not found.**

PRO questionnaires

The following PRO questionnaires will be included in the patient questionnaire packet.

Health Assessment Questionnaire Disability Index (HAQ DI)

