**DOCUMENT HISTORY**

| Version # | Issue Date | Author/Editor | Sections Changed | Change Summary   |
|------------------|-------------------|----------------------|-------------------------|---|
| V0.4             | 30 May, 2019      | [REDACTED]           | Section 2, 5            | 
 
1. Add median (Q1, Q3) for describing continuous variables when normality is violated.
 
2. Use Q1, Q3 to replace 95% Confidence interval of mean, due to the violation of normality.
 
3. Added paired Wilcoxon signed-rank test as an alternative test for paired t-test when normality is violated.
 
  |
| V0.3             | 24 Dec, 2018      | [REDACTED]           | Section 2, 5            | 
 
1. Added paired Wilcoxon signed-rank test as an alternative test for HAQ DI and WPAI analyses, due to the violation of normality.
 
2. Changed ANOVA to ANCOVA for sensitivity analysis of HAQ DI change, because we used continuous DAS28.
 
3. Added Spearman correlation as an alternative method for association analyses, due to the violation of normality.
 
   |
| V0.2             | 2 Jan, 2018       | [REDACTED]           | Section 2, 5            | 
 
1. Patient's impression of change in RA at weeks 12 and 24 after the initiation of adalimumab has been added in the Study Objectives and Statistical Analysis Section according to protocol.
 
2. Disease status of RA (moderate, severe, missing) has been deleted in Table 2, since it's duplicated with DAS28 categorization.
 
3. Dosage of first adalimumab injection has been deleted in Table 2, since the DOSE should be 40MG for all adults.
 
 |
| V0.1             | 8 Aug, 2017       | [REDACTED]           | All                     | Initial Version   |

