#### **3.2.1 Inclusion Criteria**

Patients meeting all of the following inclusion criteria at baseline will be included:

- Subject has a diagnosis of RA as defined by the 1987 revised ACR classification criteria and/or the ACR/ the European League against Rheumatism (EULAR) 2010 classification criteria (any duration since diagnosis)
- Male or female subjects  $\geq 18$  years of age (local definition according to adalimumab label) who is in compliance with eligibility for adalimumab based on the local label
- Patients with moderate to severe RA defined as DAS28 (ESR) or DAS28 (CRP)  $> 3.2$
- Biologically treatment naïve and initiated adalimumab at baseline visit
- Availability of clinical data of the previous 12 weeks prior to baseline
- Ability to self-complete patient questionnaires
- Subject must be able and willing to provide written informed consent and comply with the requirements of this study protocol

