## 5.2 Analysis Plan for Demographic and Clinical Characteristics

- Descriptive statistics will be presented for patient demographics (Excel Table 1), and clinical characteristics (Excel Table 2) for all patients. The following measures will be assessed as of the patient’s baseline:
  - Patient age (mean, SD, minimum, maximum, median; categories: 18-34, 35-44, 45-54, 55-64, 65-74, 75+, missing)
  - Gender (male, female, missing)
  - Marital status (married, unmarried, missing)
  - Medical insurance type (National/Public insurance, Private insurance, Employer benefits, other, no insurance, missing)
  - Disease Activity Score in 28 joints - DAS28 (mean, SD, minimum, maximum, median; categories: Remission, Low Disease Activity, Moderate Disease Activity, High Disease Activity, Missing)
  - Number of patients with each of the comorbidities at baseline visit (See 3.5.2), and number of patients with any of these comorbidities

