## 5.5 Analysis Plan for Exploratory Objectives

- Excel Table 7 describes the change in 4 patient satisfaction questions at weeks 12 and 24 after the initiation of adalimumab, in those patients continuing on adalimumab (observed population). These changes will be summarized as number and percentage of each response and compared with Wilcoxon signed rank test. Satisfaction will also be dichotomized and analyzed over time with Cochran-Armitage test for trends.
- Excel Table 8 summarizes the patients' global impression of change in RA at weeks 12 and 24 after the initiation of adalimumab, in those patients continuing on adalimumab (as observed population). Each response (very much better, much better, a little better, no change, a little worse, much worse, and very much worse) will be summarized as number and percentage.
- Descriptive statistics will be presented for post-index overall RA related direct healthcare resource utilization (Excel Table 9)
  - Consultations/visits to healthcare professionals for treatment of RA (number of patients with  $\geq 1$  visit; categorized by the treatment department listed in 3.5.4)
  - Procedures received when visiting the healthcare professional(s) for treatment of RA (number of patients with  $\geq 1$  procedure; categories listed in 3.5.4)
  - surgeries received when visiting the healthcare professional(s) for treatment of RA (number of patients with  $\geq 1$  surgery; categories listed in 3.5.4)
  - Hospitalizations in relation to RA (number of patients with  $\geq 1$  admission)
  - Length of stay in days (mean, SD, median)
  - Concomitant medications taken for RA (number of patients with  $\geq 1$  medication; categories listed in 3.5.4))

- Associations between disease severity (measured by DAS28) and PROs (HAQ DI score, SF-36 domain scales, EQ-5D-3L index, WPAI outcomes) will be analyzed using the bivariate linear regression model (Excel Table 10.1). Separate models will be estimated to identify the association between DAS28 and each of the PROs. If normality assumption for the residual of regression is violated, Spearman correlation coefficients and p-values will be estimated instead.

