- Additionally, in Excel Table 10.2, separate bivariate linear regression models will be estimated to identify the association between change in DAS28 and change in each of the PROs at 12 and 24 weeks after baseline respectively. If normality assumption for the residual of regression is violated, Spearman correlation coefficients and p-values will be estimated instead.
- In Excel Table 11, separate multivariate generalized linear models (GLM) will be estimated to test for the differential changes in primary and secondary efficacy outcomes after baseline, across the subgroups defined by the potential modifiers, including age, gender, baseline severity, and other diagnoses/comorbidities.

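### SAP 3.5.2 scores DAS28 with one equation that puts CRP in the ESR position, contradicting the protocol's separate DAS28(CRP) equation and mis-scoring CRP-scored patients in the supportive analyses

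*SAP*

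**What the plan says.** Protocol 9.2.4.7 defines two scores. DAS28(ESR) uses 0.70·ln(ESR) and has no constant. DAS28(CRP) has the same joint-count terms but ends in "0.36 * \ln(\text{CRP}+1) + 0.014 * (\text{Patient Global assessment of Health in mm})+0.96".

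SAP 3.5.2 gives one equation for both markers, ending in "0.70 * \ln(\text{ESR or CRP}) + 0.014 * (\text{Global assessment of Health". It has no +1 inside the logarithm and no 0.96, and it omits the unit (mm) for the global assessment. The same section lists ESR in mm/hour and CRP in mg/L, and allows either to be measured. The inclusion criteria in SAP 3.2.1 still name two scores: "Patients with moderate to severe RA defined as DAS28 (ESR) or DAS28 (CRP"), with a limit of more than 3.2. Both documents apply the same class limits of 2.6, 3.2 and 5.1.

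On the source of the value, SAP 3.5.2 has site staff "mark each component score on the CRF and the DAS28 score if calculated". It does not say whether that entry or a recomputed score is analysed.

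DAS28 is used in these places:
- Excel Table 2 (SAP 5.2), as a summary and by class: "categories: Remission, Low Disease Activity, Moderate Disease Activity, High Disease Activity, Missing".
- The HAQ DI sensitivity analysis (SAP 5.3). The V0.3 entry in the document history reads: "Changed ANOVA to ANCOVA for sensitivity analysis of HAQ DI change, because we used continuous DAS28".
- Excel Table 10.1 (SAP 5.5): "Associations between disease severity (measured by DAS28) and PROs".
- Excel Table 10.2 (SAP 5.5), with models to "identify the association between change in DAS28 and change in each of the PROs".
- Excel Table 11 (SAP 5.5), where baseline severity is one of the effect modifiers.

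**The concern.** The two documents give different scores for the same CRP-scored patient. Protocol 9.7.1 requires analyses to follow the approved SAP, so the SAP equation is the operative one unless it is corrected.

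The discrepancy is not a constant shift. It changes sign and grows towards both ends of the CRP range, so it does not cancel in a regression slope, a correlation or a change from baseline. A patient who met the entry criterion on the protocol's DAS28(CRP) could be tabulated as having low disease activity. Falls in CRP count for more in the DAS28 change than the protocol intends. CRP-scored and ESR-scored patients are also pooled after only the CRP group has been scored on an equation that the protocol does not assign to it.

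**Working it through.** The plan states no figure that depends on this equation, so there is none to reproduce. The check evaluates both printed equations for one CRP-scored patient.

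**Inputs from the documents.** Acute-phase part in the SAP: 0.70·ln(CRP). In the protocol: 0.36·ln(CRP+1) + 0.96. Class limits: 2.6, 3.2, 5.1. CRP in mg/L, from SAP 3.5.2; the protocol equation states no unit for CRP.

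**Assumed inputs.** The CRP values, joint counts and global scores below.

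**Step 1: difference in score.** With the global assessment in mm in both equations, the joint and global terms cancel:

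d(CRP) = 0.70·ln(CRP) − 0.36·ln(CRP+1) − 0.96

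| CRP (mg/L) | SAP part | Protocol part | d |
|---|---|---|---|
| 1 | 0.00 | 1.21 | −1.21 |
| 5 | 1.13 | 1.61 | −0.48 |
| 10 | 1.61 | 1.82 | −0.21 |
| 20 | 2.10 | 2.06 | +0.04 |
| 30 | 2.38 | 2.20 | +0.19 |
| 50 | 2.74 | 2.38 | +0.36 |
| 100 | 3.22 | 2.62 | +0.60 |

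d = 0 at CRP = 17.8. At CRP = 0 the SAP expression is undefined, while the protocol's is 0.96. For ESR-scored patients d = 0 throughout.

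**Step 2: class shifts.** A SAP class limit L corresponds to L − d on the protocol scale.
- CRP 5: 3.2 + 0.48 = 3.68 and 5.1 + 0.48 = 5.58. Protocol scores above 3.2 and up to 3.68 (eligible, moderate) become low; those above 5.1 and up to 5.58 (high) become moderate.
- CRP 10: the upper ends of these bands are 3.41 and 5.31.
- CRP 50: 5.1 − 0.36 = 4.74. Scores above 4.74 and up to 5.1 (moderate) become high.

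Example with 6 tender joints, 5 swollen joints and a global score of 50 mm: 0.56·√6 + 0.28·√5 + 0.014·50 = 2.70. At CRP 1 the protocol gives 2.70 + 1.21 = 3.91 (moderate, eligible) and the SAP gives 2.70 (low). At CRP 50 the scores are 5.07 (moderate) and 5.44 (high).

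**Step 3: change scores.** The constant drops out, but the slope on CRP does not. The ratio of the CRP parts is 0.70·ln(a/b) ÷ [0.36·ln((a+1)/(b+1))]:
- 100 to 10: 1.61/0.80 = 2.02
- 30 to 5: 1.25/0.59 = 2.12
- 30 to 1: 2.38/0.99 = 2.41
- 5 to 1: 1.13/0.40 = 2.85

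The total change is inflated less, because the joint and global terms are common to both equations. Assume tender joints 10 to 4, swollen joints 8 to 3 and global 60 to 30 mm. The common fall is then 3.40 − 2.02 = 1.38.

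| CRP change | SAP total fall | Protocol total fall | Ratio |
|---|---|---|---|
| 10 to 5 | 1.86 | 1.60 | 1.2 |
| 30 to 5 | 2.63 | 1.97 | 1.3 |
| 30 to 1 | 3.76 | 2.36 | 1.6 |

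**Step 4: how often classes change, under assumptions.** The simulation took log-normal CRP with median 5 to 20 mg/L and log-SD 1.0 to 1.3, mean joint counts of 8 tender and 6 swollen, and a global score around 55 mm (SD 20). Among CRP-scored patients eligible on the protocol equation, about 14% to 31% changed class and about 3% to 21% fell to 3.2 or below. These percentages depend on the assumed distributions and are not estimates for this study.

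**The case against.** The strongest reply is that the harm depends on two unknowns: how many patients were scored on CRP (possibly none), and whether the analysed value comes from the SAP formula or from the score entered on the CRF, for which sites are pointed to an online calculator. That is fair, and it limits the size of the problem. It does not remove it: the CRF entry is optional, the SAP says the score is to be derived by its printed formula, and both documents plan for CRP scoring.

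Other objections stand in part.
- Tables 10.1 and 10.2 switch to Spearman correlation if residuals are not normal. The fold inflations describe the scores and do not carry over to a rank coefficient. Ranks still move, because the error varies with CRP and changes sign.
- For Table 11 the SAP does not say whether baseline severity is continuous DAS28 or a class, so the effect there is less certain.
- The silence of the SAP's document history on a formula change proves little, because a formula present since V0.1 would not be listed.
- The undefined score at CRP = 0 matters only if such a value is recorded; the ESR equation has the same limit at ESR = 0.
- The protocol accepts either marker and has no rule that a patient keep the same one, so a one-marker rule is advice and not part of the contradiction.

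The primary and main secondary HAQ DI tests do not use DAS28.

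**Conclusion.** The concern holds. The SAP equation contradicts the protocol's DAS28(CRP) equation and, applied as written, mis-scores CRP-scored patients by about −1.2 to +0.6 points over CRP 1 to 100 mg/L. That is enough to cross the 3.2 and 5.1 limits and to inflate a total DAS28 change 1.2- to 1.6-fold in the worked cases. Here, mis-scored means relative to the protocol's own equation, with CRP in mg/L. The contradiction needs no assumption; the sizes rest on assumed CRP, joint and global values.

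The effect is confined to supportive analyses: severity classes in Table 2, the associations in Tables 10.1 and 10.2, the severity modifier in Table 11, and the covariate slope and interval width in the sensitivity ANCOVA. The adjusted mean from that one-group ANCOVA is unaffected if it is evaluated at the covariate mean, which the SAP does not state, and if no patient is lost through CRP = 0. This should be fixed, but it does not threaten the primary result.

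**What to change.** 1. Replace the equation in SAP 3.5.2 with the protocol's two equations, keeping the global assessment in mm and stating CRP in mg/L.
2. Add one sentence saying whether the analysed DAS28 is recomputed from its components or taken from the CRF, and which version applies to each patient.
3. If the SAP formula was programmed, correct the derived variable and rerun Excel Tables 2, 10.1, 10.2 and 11 and the sensitivity ANCOVAs at weeks 12 and 24.
4. Optional: where the data allow, use one marker within a patient, and flag patients whose marker changes between visits.

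The cost is one formula correction, one sentence and, if needed, one reprogrammed variable with reruns. The formula fix needs no new data; patients with mixed markers are flagged and not measured again.
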